5. For Time Controls: Are currently pregnant or lactating, or are of child-bearing potential or are likely to become pregnant during the study and unwilling to use contraception; Acceptable forms include:
 - a. Barrier methods (such as a condom or diaphragm) used with a spermicide (a foam, cream, or gel that kills sperm)
 - b. Copper IUD
 - c. Hysterectomy
 - d. Tubal ligation
 - e. Abstinence (no sex)
6. Any condition or factor judged by the investigator to preclude participation in the study

Study Design and Procedures: This will be a randomized open-label trial. Participants will be randomized 1:1 to one of 2 groups, distinguished by the **estradiol replacement therapy regimen**. One group will receive the standard 100 mcg or lower transdermal estradiol patch as clinically indicated (or an equivalent oral dose; n=up to 25). The other group will be on transdermal (or oral) estradiol therapy titrated to achieve a serum estradiol level of 80-120 pg/ml (n=up to 25). Participants with an intact uterus will also be prescribed a progestogen for endometrial protection. A third group of healthy age-matched premenopausal women, not on any hormonal contraception will be recruited via an advertisement, and will be studied as time controls (n=up to 10).

The women deemed eligible based on the phone screen will be scheduled for a baseline medical assessment by an MD in the Mayo Clinic Menopause and Women's Sexual Health Clinic (MWSH). This is a normal part of clinical care for these women prior to oophorectomy. This visit will occur after they have been evaluated in the Department of Gynecology, and a decision to proceed with bilateral (or completion) oophorectomy has been made. Relevant past history including history of pregnancy induced hypertension and gestational diabetes will be obtained. If the patient is eligible and interested in study participation, they will meet with a study team member who will review the informed consent and answer all of the patients' questions.

After they agree to participate and sign the consent form, they will complete questionnaires to assess the following (these questionnaires will also be assessed at 6 and 12 month visits):

- a. *Menopausal symptoms severity: Menopause Rating Scale (MRS)*. This self-reported questionnaire consists of 11 items covering psychological, somatic, and urogenital subscales. It can be easily administered and scored, and completed in less than 5 minutes.

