We will ask participants to collect 24h urine sample. A mail-in kit will be sent to the participant, and clear instructions for collection will be provided. Participants on any kind of exogenous glucocorticoid therapy will be excluded from this part of the study. Urine samples will be aliquoted and stored as a part of the IRB # 13-005838 biobank. Urine steroid profiling will be performed in batches in the ICL lab.

The participants will then be asked to report to the clinical research and trials unit (CRTU) for the baseline study visit. When they report to the CRTU for the baseline visit, they will be in the fasting state (8 hours) to complete the tests listed below. Participants will also refrain from vigorous exercise, caffeine, and alcohol for 24 hours prior to the study days.

[figure not shown]
Baseline Study Day Protocol:

1. ***Urine Pregnancy Test:*** Urine Pregnancy tests will be performed on subjects determined to be of child-bearing potential. Nurses in the CRTU will assess the need for this, and confirm through a pregnancy test their status before beginning physiological testing.
2. ***Blood sampling:*** Baseline blood samples will be collected for estradiol, estrone, testosterone (total and free), glucose, insulin, lipid panel, norepinephrine, a bone alkaline phosphatase and HbA1c. We will also plan to store 5 ml each of serum and plasma for future testing, including genomic studies.. The norepinephrine test will be omitted for the limited participation subjects.
3. ***Dual energy x-ray absorptiometry (DXA):*** Body composition will be measured prior to the study visit in the CTSA body composition core using DXA. All subjects will have whole-body and regional fat and fat-free mass measured by regional analysis of whole-body DXA scans with Lunar software. (Baseline DXA scan for the limited participation subjects can be done within a month after oophorectomy.)

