the same way as done for the baseline visit. A 24-hour urine sample will be collected again in a mail-in kit as described above. Participants on any kind of exogenous glucocorticoid therapy will be excluded from this part of the study. Urine samples will be aliquoted and stored as a part of the IRB # 13-005838 biobank. Urine steroid profiling will be performed in batches in the ICL lab.

Time controls will complete baseline, 6 month, and 12 month study visits.

Participant Retention: All participants will be remunerated up to \$300. Participants will be remunerated \$100 for each of the following visits: baseline, six months and twelve months. If a participant refuse the cardiovascular testing, and chooses the option to complete the blood-work, questionnaires and DXA scan only, they will be remunerated \$50 for each of the following visits: baseline, six months and twelve months. Amounts will be prorated according to the visits the participant completes. In addition, participants will be provided with Mayo parking vouchers for the time they are onsite for study visits. For CRTU visits, participants will be given six-hour vouchers, and for other visits participants would be given 2 hour parking vouchers. After the long visits in the CRTU, which requires fasting for 8 hours, participants will be provided a meal.

Statistics (prepared in collaboration with [name], Ph.D.): For the proposed investigation, women 21-45 years of age undergoing bilateral oophorectomy will be randomized to one of two groups, based on the regimen of estradiol replacement therapy (standard versus titrated). In addition to estradiol, patients who do not undergo hysterectomy will receive a progestogen as clinically indicated. A randomization schedule will be generated by the Section of Biostatistics using varied blocked randomization to attain an equal number of women assigned to each treatment group. Covariates not balanced through randomization, such as additional hormone use in patients with hysterectomy, will be accounted for in analysis. For all aims, the primary analyses will be performed using intention to treat with **estradiol dosing regimen** as the *treatment group variable* and secondary analyses will be performed using the **serum estradiol concentration (E2)** as a *continuous explanatory variable*.

Statistical Analysis:

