Aims 1 and 3: We will first perform cluster analysis among the variables to identify set of variables that are highly correlated, and regression analysis to identify the dependency between the outcome variable and its covariate. We will also perform a multivariable regression analysis taking into account all the covariates and applying penalized methods such as least absolute shrinkage selection operator (lasso) [17] for covariate selection.

Aim 2: We will plot the data to identify the patterns between the outcome variable and the covariates. We will then fit a mixed-effects model with two fixed effects parameters, the intercept and the slope of the linear trend for the population, and two random effects for each participant, i.e., the deviations in intercept and slope of that participant's time trend from the population values.

Power calculation: The analysis of the 12 month outcomes will be considered the primary analysis, with analyses of the earlier time point used to supplement the primary findings. In all cases, distributional assumptions will be assessed with transformations or non-parametric methods used as appropriate. When the direction of a difference is hypothesized a priori (e.g. women receiving the lower dose of estradiol will have poorer endothelial vasodilator function) a one-tailed test will be used; if the direction is not stated a two-tailed test will be used.

Sample-size/statistical power considerations: In general, a sample-size of N=25 per group will provide statistical power (one-tailed, alpha=0.05) of 82% to detect a difference between groups of 0.75 standard deviation units. Therefore, although preliminary data are not available for each aim and the statistical power will differ for the multiple facets of each aim, we believe that a sample-size of N=25 per group will provide adequate statistical power to test both our primary and secondary hypotheses.

Investigative Sequence and Timeline:

Year	Aims	Number of Studies (Total = 150)
1	1 and 2	~50 (~15-18 participants and 3 visits each)
2	1 and 2	~50 (~15-18 participants and 3 visits each)
3	1 and 2	~50 (~15-18 participants and 3 visits each)

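### Aims 1 and 3: the primary 12-month between-arm model is not written out, its adjusters are chosen from the trial data, and the baseline outcome already collected is not fixed in it

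*Combined protocol and SAP*

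**What the plan says.** The Statistics section sets the primary comparison: "For all aims, the primary analyses will be performed using intention to treat with" dosing regimen as the group variable. The Power calculation paragraph sets the time point: "The analysis of the 12 month outcomes will be considered the primary analysis".

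The adjustment rules are in two places.
- Statistics: "Covariates not balanced through randomization, such as additional hormone use in patients with hysterectomy, will be accounted for in analysis". No list of covariates and no threshold for imbalance is given.
- Statistical Analysis, Aims 1 and 3: cluster analysis, then regression to find which covariates the outcome depends on, then "We will also perform a multivariable regression analysis taking into account all the covariates and applying penalized methods such as least absolute shrinkage selection operator", for the purpose of covariate selection. The covariates are not listed. There is no rule for the penalty, no statement of which terms stay unpenalised, and no method of inference after selection.

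The baseline outcome is available, because the 12-month visit repeats the baseline study-day protocol. The one remark on using it is under Limitations: each participant acts as her own control, and baseline is compared with values on therapy. The mixed model in the Statistical Analysis section belongs to Aim 2. Its fixed effects are an intercept and a time slope, so it does not supply the missing between-arm model.

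**The concern.** In a trial of 50 randomised women, the baseline value of a physiological outcome is usually the most useful adjuster, and here it has already been paid for. The plan leaves three readings open: an unadjusted contrast, a change-score contrast suggested by the Limitations remark, or a regression whose adjusters are picked after the data are seen. The first two give up precision, by an amount that depends on the correlation between baseline and 12 months. The third makes the result depend on an adjustment set unknown in advance and, if ordinary standard errors are reported after selection, can make the test somewhat too liberal.

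**Working it through.** **Inputs.** From Sample-size/statistical power considerations: 25 per group, difference 0.75 SD, one-tailed alpha 0.05, stated power 82%. The documents give no baseline-to-12-month correlation r, so r = 0.3, 0.5, 0.6 and 0.7 are assumed. Dropout is not modelled.

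**Step 1: the plan's own figure.** Two-sample t-test, SD = 1, 48 df. Noncentrality = 0.75 × √(25/2) = 2.652; critical value 1.677; power 83.4%. This is within 2 points of 82%; the two-sided version gives 73.8%. The stated power therefore corresponds to an unadjusted one-tailed comparison.

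**Step 2: ANCOVA and change scores.** ANCOVA: residual SD = √(1 − r²), SE = √(2/25) × √(1 − r²), noncentrality = 0.75 × √(25/2) / √(1 − r²), 47 df. Chance baseline imbalance multiplies the variance by 1 + 1/46. Change score: SD = √(2(1 − r)), 48 df.

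| r | ANCOVA SE (unadjusted 0.283) | ANCOVA power | allowing for chance imbalance | change-score power |
|---|---|---|---|---|
| 0.3 | 0.270 | 86.3% | 85.7% | 71.4% |
| 0.5 | 0.245 | 91.5% | 91.0% | 83.4% |
| 0.6 | 0.226 | 94.8% | 94.4% | 89.9% |
| 0.7 | 0.202 | 97.8% | 97.6% | 95.8% |

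In sample-size terms, 25/(1 − r²) gives 27.5, 33.3, 39.1 and 49.0 women per arm in an unadjusted analysis. At r = 0, ANCOVA allowing for chance imbalance gives 82.7%, a loss of 0.7 point.

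**Step 3: what lasso would do if it were the primary model.** The number of candidates must be assumed. The protocol collects at least 18 baseline measures besides the outcome:
- eight questionnaire scales ("they will complete questionnaires to assess the following (these questionnaires will also be assessed at 6 and 12 month visits");
- ten blood measures, counting the lipid panel as one ("Baseline blood samples will be collected for estradiol, estrone, testosterone (total and free), glucose, insulin, lipid panel, norepinephrine, a bone alkaline phosphatase and HbA1c").

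The simulation used 5,000 trials per r. The arm was unpenalised, and baseline was offered with 18 candidates unrelated to the outcome. The penalty was the minimum-error one from 5-fold cross-validation, followed by an ordinary least-squares refit. The plan's preliminary cluster step was not simulated.
- Type I error at r = 0.3/0.5/0.6/0.7: 6.8/7.1/7.8/7.2%, against 5.3/4.8/5.0/4.8% for ANCOVA on the same data. Monte Carlo error is 0.3 to 0.4 point.
- Mean reported SE 0.263/0.237/0.218/0.195, against an actual spread of 0.294/0.271/0.254/0.225.
- With the one-standard-error penalty: 5.7/5.9/6.3/5.6%.
- With 4 other candidates, in separate runs of 2,500 trials: 5.4%.

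**Step 4: does fixing baseline alone cure this?** No. In the separate 2,500-trial runs with 18 candidates, type I error at r = 0.3/0.5/0.7 was 6.8/7.0/7.0% with baseline as a lasso candidate. It was 6.4/7.0/7.0% with baseline forced in and lasso choosing the rest. The inflation comes from selecting among the other covariates.

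**The case against.** The strongest reply is that nothing here makes the primary comparison invalid. The lasso sentence says the regression will also be performed, so it can be read as supplementary. The primary analysis would then be the plain randomised contrast, which is valid and matches the power statement. The Limitations section shows that the investigators mean to use baseline, and the study is described as a source of pilot data. This stands: on that reading there is no inflation, only precision forgone. What remains is that no between-arm model is stated for these aims, and the imbalance rule in the Statistics section would still be data-driven.

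A second reply is that lasso would usually find baseline unaided. In the 18-candidate simulation it kept baseline in 51/93/99/100% of trials. Power was 85.0/89.9/93.2/96.7%, against 85.9/91.3/93.7/97.6% for ANCOVA on the same data. So if baseline is offered as a candidate, most of the power gain is recovered.

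Third, the inflation is modest and sensitive to the set-up. A small run of 800 null trials with ten candidates gave 4.1% at r = 0.3 and 5.1% at r = 0.6; there the arm was penalised during selection and then forced into the refit. Runs of 4,000 trials with ten candidates gave 6.0% and 6.1%.

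A reader might also infer that lasso could remove the treatment term. The documents do not support that: regimen is named separately as the treatment variable, apart from the covariates to be selected.

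**Conclusion.** The point holds as a free improvement, not as an error in the plan. The omission itself is certain from the text: all stated adjustment routes are data-driven, and baseline is not fixed in the 12-month between-arm model.

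The size of the gain rests on the assumed r and on the comparator. Over r = 0.3 to 0.7, ANCOVA adds 2.9 to 14.4 points of power to the unadjusted analysis (2.3 to 14.2 allowing for chance imbalance). Against change scores the order reverses: 14.9 points at r = 0.3, falling to 2.0 at r = 0.7.

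The type I figure of roughly 5.4 to 7.8% is conditional on lasso being the primary model and on an ordinary refit, and it varies with the number of candidates and the penalty. Three stronger inferences are not supported:
- that the trial's type I error is inflated as planned, since the documents do not settle whether lasso is primary and state no refit;
- that the 82% power is wrong, since it reproduces;
- that fixing baseline by itself would remove any inflation, since Step 4 shows otherwise.

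**What to change.** State in the Statistical Analysis section that the primary analysis of each Aim 1 and Aim 3 outcome is an ANCOVA of the 12-month value on randomised group and the baseline value of the same outcome. Both terms should be fixed in advance and unpenalised, whatever imbalance is observed. Apply the existing distributional provision ("In all cases, distributional assumptions will be assessed with transformations or non-parametric methods used as appropriate") to this same model. Label clustering, regression screening, lasso and imbalance-driven adjustment exploratory; this step, rather than the baseline term, is what protects the type I error.

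The cost is SAP wording and one degree of freedom (48 to 47), with about 0.7 point of power lost if baseline turns out to be uncorrelated with the outcome. No additional participants or measurements are needed.

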
Aim 1: Compare the cardiovascular function in young women (<46 years) following bilateral oophorectomy who are treated with either the standard dose of estradiol(100 mcg or lower transdermal patch or equivalent oral dose) or titrated estradiol dosing to achieve average premenopausal estradiol level (80-120 pg/ml).

Hypothesis: Women receiving the titrated dosing of estradiol will have better cardiovascular function than women receiving the standard dose of estradiol.

Aim 2: Characterize the relationship between the serum estradiol level and cardiovascular function in young women (<46 years) on estradiol replacement after bilateral oophorectomy.

Hypothesis: There will be a dose response relationship between the serum estradiol level and cardiovascular function.

Aim 3: Compare the body composition in young women following bilateral oophorectomy who are treated with either the standard dose of estradiol (100 mcg or lower transdermal patch or equivalent oral dose) or titrated estradiol dosing to achieve average premenopausal estradiol level (80-120 pg/ml).

Hypothesis: Women receiving the titrated dosing of estradiol will have a body composition closer to their premenopausal state as compared to women receiving the standard dose of estradiol.

Background and Significance: Bilateral oophorectomy performed before the natural age of menopause is an important cause of premature estrogen deprivation, and may not be avoidable in women undergoing surgery for gynecologic cancer or ovarian cancer risk reduction in high risk individuals, such as BRCA mutation carriers.[6] In the absence of estrogen replacement therapy, these women are at increased risk for several adverse health outcomes including CVD, cognitive dysfunction, mood disorders, osteoporosis, accelerated aging and early death. The risk for many of these conditions is higher with younger age at oophorectomy.[6] Many professional societies, therefore, support the use of estrogen therapy for these women, not only for management of menopausal symptoms, but also to mitigate the adverse long-term health consequences of bilateral oophorectomy.[8, 9] The current clinical practice is to use estrogen-based hormone therapy at least until the natural age of menopause unless there is a contraindication to its use.[1] However, in the absence of evidence regarding the impact of the specific estrogen therapy regimens on health outcomes in these women,[10]

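### The model written for Aim 2 has an intercept and a time slope but no estradiol term, so it does not test the estradiol dose-response hypothesis; the estradiol analysis announced in the Statistics section has no model

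*Combined protocol and SAP*

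**What the plan says.** **Hypothesis (Specific aims, Aim 2).** "There will be a dose response relationship between the serum estradiol level and cardiovascular function". The population is young women "on estradiol replacement after bilateral oophorectomy".

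**Model (Statistical Analysis, Aim 2).** After plotting the outcome against unnamed covariates, the plan will "fit a mixed-effects model with two fixed effects parameters, the intercept and the slope of the linear trend for the population". Each participant also has two random effects, "the deviations in intercept and slope of that participant's time trend from the population values".

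**General statement (Statistics).** For every aim the primary analysis is by randomised dosing regimen, and "secondary analyses will be performed using the serum estradiol concentration (E2) as a *continuous explanatory variable". No model, timing of estradiol, adjustment set or test is attached to this.

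**Time point and tails (Power calculation).** This paragraph ranks the visits as follows: "The analysis of the 12 month outcomes will be considered the primary analysis, with analyses of the earlier time point used to supplement the primary" result. A one-tailed test applies where a direction was hypothesised in advance; "if the direction is not stated a two-tailed test will be used".

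**Data.** At the first study visit, "Baseline blood samples will be collected for estradiol, estrone" and other analytes. The 6-month visit repeats that protocol without glucose, lipids, insulin and DXA, and the 12-month visit repeats it in full. Serum estradiol is therefore available at all three visits.

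**The concern.** The hypothesis is about estradiol and the model is about time. A statistician who fits the Aim 2 model as written will report whether cardiovascular function changed between the preoperative visit and 12 months. That change mixes the effects of oophorectomy, treatment and elapsed time. It does not show whether women with higher estradiol have better function.

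The general statement on estradiol shows what is intended but leaves the model open. The timing of estradiol, the visits used, the adjustment and the coefficient to be tested could then all be settled after the data are seen. The general statement also ranks the estradiol analysis as secondary for every aim, although in Aim 2 estradiol is the exposure of interest.

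**Working it through.** **1. The plan's own power figure.** The sample-size paragraph gives 82% power for 25 per group, a difference of 0.75 SD and one-tailed alpha 0.05. A two-sample t test has noncentrality 0.75 × √(25/2) = 2.65 on 48 degrees of freedom, and its power is 83.4%. The figure reproduces approximately. It concerns a difference between two group means and says nothing about an estradiol coefficient.

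**2. Terms of the Aim 2 model.** Written out, it is

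Y(i, t) = b0 + b1·t + u0(i) + u1(i)·t + e(i, t).

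The fixed effects are b0 and b1. Neither is a coefficient on estradiol or on regimen.

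**3. What b1 estimates.** With complete data at t = 0, 6, 12 and the same columns (1, t) in the fixed and random parts, the generalised least squares slope equals the ordinary least squares slope. Its weights are (t − 6)/Σ(t − 6)² = (−6, 0, 6)/72 = (−1/12, 0, +1/12). Hence

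b1 = (mean at 12 months − mean at baseline)/12, pooled over both arms.

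A numerical check over 1,000 random variance settings gave these weights, with deviations below 1e-12. The 6-month visit has zero weight, and the baseline visit, before surgery and replacement, supplies one end of the contrast.

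**4. How estradiol could enter b1.** Suppose the true mean is a + γ·t + β·E2. Then the expected slope is γ + β × (mean E2 at 12 months − mean E2 at baseline)/12. Estradiol contributes only through its mean change and cannot be separated from γ. If the mean level at 12 months equals that at baseline, β drops out whatever its size.

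**5. Illustration for the time slope (assumed values).** Take 50 women, outcome SD 1, two-tailed 0.05. For baseline-to-12-month correlation r, the SD of the change is √(2(1 − r)), which is 1.00 at r = 0.5 and 0.775 at r = 0.7. The noncentrality is the mean change × √50 divided by that SD.

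| Mean change (SD) | 0 | 0.25 | 0.5 |
|---|---|---|---|
| Slope significant, r = 0.5 | 5% | 41% | 93% |
| Slope significant, r = 0.7 | 5% | 61% | 99% |

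In simulation with r = 0.5 these rates moved by at most 1 point as the estradiol partial correlation went from 0 to 0.5. That follows from the model's form; it illustrates step 3 and is not separate evidence.

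**6. Illustration for an estradiol coefficient (assumed values).** Regress the 12-month outcome on 12-month estradiol and the baseline outcome, two-tailed 0.05. Simulated power:

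| Partial correlation | 0.3 | 0.4 | 0.5 |
|---|---|---|---|
| N = 50 | 56% | 82% | 96% |
| N = 40 | 46% | 72% | 92% |
| N = 30 | 37% | 58% | 80% |

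The approximation Φ(atanh(ρ) × √(N − 4) − 1.96) agrees within 2 points. For example, at ρ = 0.4 and N = 50 it is Φ(0.4236 × 6.782 − 1.96) = Φ(0.913) = 82%. Only N = 50 comes from the documents. It is a best case: Study Design and Procedures says up to 25 per arm, and women who refuse cardiovascular testing may join for blood work, questionnaires and DXA only. These figures belong to the 12-month regression, not to a two-visit mixed model.

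**7. Visits and random slope.** At 6 and 12 months only, a 2 × 2 covariance matrix supplies 3 distinct quantities for 4 variance parameters (two variances, one covariance, the residual). A random slope is then not identified. With three visits, all 4 parameters are identified.

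**The case against.** The best defence is that the estradiol analysis is already planned. The general statement stands just before the Aim 2 paragraph and covers all aims, so a statistician who reads both would put estradiol in the model. The initial plot against covariates also allows the mixed model to be read as a base growth model to be extended.

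Part of this stands. A reader might infer that the plan has no estradiol analysis, or that Aim 2 cannot be answered. The documents do not support that, because the commitment is explicit and the data are collected. What does not stand is that the commitment supplies the model. The Aim 2 paragraph counts its fixed effects as two and calls the slope a time trend, so it cannot be read as a slope on estradiol. The plot yields no test, and the multivariable regression with lasso is listed for Aims 1 and 3 only.

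A second objection concerns tails. The Aim 2 hypothesis states no direction, which under the plan's rule points to a two-tailed test. But the rule's own example of a stated direction is lower estradiol dose with poorer vascular function, and Aim 1 predicts better function with titration. A reader might take two-tailed as settled; it should be declared.

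A third is weight: the estradiol analyses are labelled secondary, the aim is to characterise a relationship, and the sponsor describes the results as pilot data. That limits the seriousness of the point but not its correctness.

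**Conclusion.** The point holds as a mismatch between aim and model. None of the two fixed effects written for Aim 2 bears on its hypothesis, and the announced estradiol analysis has no model. This rests on the wording and on no power figure. The identity in step 3 assumes complete data at common visit times; with missing visits the weights would change, but the model would still have no estradiol term.

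It should be fixed before analysis, but it does not undermine the trial. Aim 1's randomised comparison is untouched. A reader might also infer from step 6 that Aim 2 is adequately or inadequately powered. The documents give no estradiol slope or SDs, so power cannot be derived from them; the figures are illustrations under assumed correlations.

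**What to change.** - **Statistical Analysis, Aim 2:** add serum estradiol as a fixed effect and name its coefficient as the Aim 2 test. To respect the plan's time-point rule, make the main estimate the 12-month outcome on 12-month estradiol, adjusted for the baseline outcome. It compares women with each other.
- **Supporting analysis:** a mixed model of the 6- and 12-month visits, when women are on replacement, with concurrent estradiol, visit, baseline outcome and a random intercept only. Its coefficient also uses change within women.
- **Statistics:** state that estradiol is the main explanatory variable for Aim 2, so that the two sections agree.
- **Tails:** state the choice in advance: two-tailed under the plan's rule, unless the sponsor declares a direction.
- **Reporting:** describe the result as an observational association. Achieved estradiol is not randomised, and under Surgery and dismissal the dose in the standard group may follow symptoms.

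The cost is rewording two paragraphs and a small re-specification. No new data are needed, and Aim 1 does not change.
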